13.2.1 Safety Completeness

Analysis Solicited Adverse Events

The safety completeness analysis on solicited AEs aims to identify subjects who completed the electronic diaries, irrespective of severity. The analysis will show the number of subjects with results by solicited AE and day.

Three summaries will be produced:

1. The frequencies of subjects who provided data on the electronic diary cards by vaccine group.
2. For each solicited AE – including analgesic use, the frequencies of subjects with data will be presented by vaccine group and day.

3. For each solicited AE – including analgesic use, frequency of the number of days with data on the eDiary by vaccine group.

For the corresponding percentages, the denominator will be the respective number of subjects vaccinated (All-Exposed Set – analyzed as treated).

13.3 Unsolicited Adverse Events

This analysis applies to all unsolicited AEs occurring during the study, judged either as probably related, possibly related, or not related to vaccination by the investigator, recorded in the AE eCRF, with a start date on (but with onset after vaccination) or after the date of vaccination.

The original verbatim terms used by investigators to identify AEs in the eCRFs will be mapped to PTs using the MedDRA dictionary.

The AEs will then be grouped by MedDRA PTs into frequency tables according to SOC. All reported AEs, as well as AEs judged by the investigator as at least possibly related to study vaccine, will be summarized according to SOC and the PT within SOC. These summaries will be presented by the vaccine group and by interval of study observation (Day 1-Day 22, Day 23-EOS, Day 1-EOS). When an AE occurs more than once for a subject, the maximal severity and strongest relationship to the vaccine will be counted.

The assignment to time intervals will be done by day of onset.

The AE summaries will be presented by SOC and PT and different periods of onset depending on the category of events.

- Unsolicited AEs during the 30 minutes post vaccination
- SAEs
- Unsolicited AEs that are possibly or probably related to vaccine
- AESIs
- AEs leading to withdrawal
- Deaths

All tables will be produced by treatment.

An overview summary of AEs, including frequencies and percentages of any AEs (by mild/moderate/severe grade), related AEs, AEs leading to withdrawal, any SAEs, related SAEs, AESIs and deaths will also be presented.

In addition, summary of subjects with unsolicited non-serious adverse event reported by >5% of subjects and summary of subjects with unsolicited non-serious or solicited adverse event reported

by >5% of subjects in any vaccine group sorted by SOC and PT will be provided for clinicaltrials.gov and EudraCT.eu posting purposes.

Separate data listings of all AEs, SAEs, AESIs, AE leading to withdrawal and AE leading to death will be provided by study treatment, subject and onset date.

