The use of analgesics/antipyretics will be captured as “absent” or “present” separately by reason “for treatment” or “for prevention”.

Note: Any solicited AE that meets any of the following criteria must be entered into subjects’ source document (see [Section 9.1, Source Documentation](#)) and also as an AE on the AE eCRF:

- Solicited local or systemic AE leading to the subject withdrawing from the study or the subject being withdrawn from the study by the investigator (AE leading to withdrawal, see [Section 7.1.3, Evaluation of Adverse Events](#)).

Protocol Number: V118_23

Product Name: aQIV

Document Status: Final Version 3.0, Document Date: 11 Jul 2022

- Solicited local or systemic AE that otherwise meets the definition of an SAE (see [Section 7.1.4, Serious Adverse Events](#)).

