7.1.2 Unsolicited Adverse Events

An unsolicited AE is an AE that was not solicited using a Subject eDiary and that was spontaneously communicated by a subject who was vaccinated.

Potential unsolicited AEs may be medically attended (defined as symptoms or illnesses requiring hospitalization, or emergency room visit, or visit to/by a qualified healthcare professional) or were of concern to the subject. In case of such events, subjects will be instructed to contact the site as soon as possible. The detailed information about the reported unsolicited AEs will be collected by the qualified site personnel during the interview and will be documented in the subject's records. In this study, all unsolicited AEs will be collected during the treatment period (Day 1-Day 22), and only specific unsolicited AEs (SAEs, AEs leading to withdrawal and AESIs) will be collected during the follow-up period (Day 23-Day 271). In addition, any unsolicited AEs reported within 30 minutes after the study vaccination will be collected as immediate postvaccination AEs.

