8.1.2.1 Secondary Safety Endpoint(s)

Safety and reactogenicity will be assessed by the frequency and severity of:

- Solicited local and systemic AEs for 7 days following vaccination (Day 1 through Day 7);
- All unsolicited AEs for 21 days following vaccination (Day 1 through Day 22);
- SAEs, AEs leading to withdrawal from the study, AESIs as collected from Day 1 through Day 271.

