8.4.3.1.3 Analysis of Unsolicited Adverse Events

This analysis applies to all AEs occurring during the study, judged either as probably related, possibly related, or not related to vaccination by the investigator, recorded in the AE eCRF, with a start date on or after the date of vaccination. The original verbatim terms used by investigators to identify AEs in the eCRFs will be mapped to preferred terms using the MedDRA dictionary. The AEs will then be grouped by MedDRA preferred terms into frequency tables according to system organ class (SOC).

All reported AEs, as well as AEs judged by the investigator as at least possibly related to study vaccine, will be summarized according to SOC and preferred term within SOC. These summaries will be presented by treatment group and by interval of study observation. When an AE occurs more than once for a subject, the maximal severity and strongest relationship to the treatment group will be counted.

Separate summaries will be produced for the following categories:

- Unsolicited AEs during the 30 minutes postvaccination;
- AEs
- SAEs;
- Unsolicited AEs that are possibly or probably related to vaccine;
- AESIs;
- AEs leading to withdrawal.

Protocol Number: V118_23

Product Name: aQIV

Document Status: Final Version 3.0, Document Date: 11 Jul 2022

Data listings of all AEs will be provided by subject. In addition, AEs in the categories above will be provided as listed data.

No imputation of missing unsolicited AEs will be used.

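### SAP 13.3's scope sentence conflicts with Protocol 8.4.3.1.3 and with the SAP's own SAE and withdrawal rows, so it is unclear whether serious or withdrawal-causing solicited reactions are counted

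*SAP*

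**What the plan says.** **Collection.** The note in Protocol 7.1.1 names two kinds of solicited reaction that must go into the source document "and also as an AE on the AE eCRF". One is "Solicited local or systemic AE leading to the subject withdrawing from the study", or being withdrawn by the investigator. The other is "Solicited local or systemic AE that otherwise meets the definition of an SAE".

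**Definition.** Protocol 7.1.2: "An unsolicited AE is an AE that was not solicited using a Subject eDiary".

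**Endpoint.** Protocol 8.1.2.1 lists "SAEs, AEs leading to withdrawal from the study, AESIs as collected from Day 1 through Day 271", with no restriction to unsolicited events.

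**Analysis, protocol.** Section 8.4.3.1.3 opens with "This analysis applies to all AEs occurring during the study, judged either as probably related, possibly related, or not related to vaccination by the investigator", goes on to require that the events be recorded in the AE eCRF, and lists SAE and withdrawal summaries among its outputs.

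**Analysis, SAP.** Section 13.3 uses nearly the same sentence but begins "This analysis applies to all unsolicited AEs occurring during the study". Beneath it are bullets for SAEs, AESIs, AEs leading to withdrawal and deaths, and an overview table with rows for SAEs, related SAEs and withdrawals. None of these is limited to unsolicited events. The bullets for the 30-minute period and for related events are.

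**The concern.** The scope sentence governs everything under SAP 13.3. If it is programmed as written, a solicited reaction that is serious or ends participation is on the AE eCRF but does not qualify for the tables meant to report it. It would still appear in SAP 13.2, but only by grade, day and duration, with nothing to show that it was serious or caused withdrawal. The reported SAE and withdrawal counts would then no longer match the endpoint in Protocol 8.1.2.1.

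The opposite choice also has a cost. If every AE eCRF record is taken, the same reaction is counted in SAP 13.2 and again in the any-AE, related-AE and severity rows of 13.3, with nothing to separate it. A prespecified plan should not leave this choice to programming.

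**Working it through.** The documents give no figure for this point, so the check is a comparison of text.

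1. **Are these reactions on the AE eCRF?** Yes. Protocol 7.1.1 requires it for both kinds, and enters them as AEs, not as unsolicited AEs.

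2. **Are they unsolicited?** Not by Protocol 7.1.2. The one stated reclassification is the Day 14 rule (Protocol 5.3, 7.1.1 and 8.4.3.1.2; SAP 13.2), under which a reaction that persists that long is captured as unsolicited. Events in the 30 minutes after injection are also collected as unsolicited AEs (Protocol 5.3 and 7.1.2), because eDiary recording starts only after that period (Protocol 3.6.2). The affected class is therefore narrow: reactions recorded in the eDiary, not carried over by the Day 14 rule, that were serious or led to withdrawal.

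3. **Does the protocol analysis cover them?** Yes on its scope sentence, which takes all AEs on the form.

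4. **Does the SAP analysis cover them?** On its scope sentence, no. On its SAE, AESI, withdrawal and death rows, read alone, yes. The introduction to SAP 13 supports the second reading, because it lists serious AEs, withdrawals and AESIs as a category separate from unsolicited AEs. But Sections 13.1 to 13.5 give that category no section of its own, so it is reported only under 13.3.

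5. **Could another SAP table report them?** No.
   - None of the nine summaries in SAP 13.2 shows seriousness or withdrawal.
   - SAP 9.1 counts study withdrawals but does not identify the AE behind them.
   - The registry-posting summaries in 13.3 cover non-serious unsolicited events, alone or together with solicited events, reported by more than 5% of subjects.

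6. **Which analysis set applies?** SAP 7.5 ties unsolicited analyses to the Unsolicited Safety Set and solicited analyses to the Solicited Safety Set; Protocol 8.4.3.1.5 does the same. Neither names a set for a table that mixes the two. SAP 7.5 already defines an Overall Safety Set as the union.

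7. **Size.** One subject in a planned arm of about 1,009 is 1/1,009 = 0.10%. The count of such subjects is not in the documents. If it is assumed to be 0 to 5 per arm, the shift is 0 to 5/1,009 = 0.50 percentage points. That range is purely illustrative.

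**The case against.** The strongest reply is that the SAP, read as a whole, already includes these events. Its SAE, AESI, withdrawal and death bullets are unqualified, its overview promises all SAEs, and its listings cover all AEs. SAP 8.7 sets out explicit exclusion flags, for events starting before vaccination and for late events that are not SAEs, AESIs or withdrawals, and has none for records that began as solicited reactions. The protocol also uses the term loosely: its own section is headed as an analysis of unsolicited events, yet it contains the SAE and withdrawal summaries. Finally, safety is descriptive, no hypothesis test is affected, and every SAE is reported within 24 hours (Protocol 7.1.5).

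Most of this stands. A reader might infer that the SAP definitely drops these reactions; the unqualified rows, SAP 13 and SAP 8.7 do not support that. But they do not settle the matter. The restriction is in the sentence that sets the scope of the section. Where 13.3 does want solicited events counted, in one registry-posting summary, it says so, which invites the inference that they are excluded elsewhere. Expedited reporting protects case-level surveillance but does not correct a table in the study report.

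A reader might also infer that any omission would fall mainly on the adjuvanted arm and hide related SAEs there. The documents give no expected counts of serious or withdrawal-causing solicited reactions in either arm. Protocol 1.3 says that most listed side effects of aQIV were mild or moderate and short-lived, and that its reactogenicity has not been assessed at 50 to 64 years. An imbalance is possible but not shown.

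**Conclusion.** The conflict is real. The SAP 13.3 scope sentence disagrees with Protocol 8.4.3.1.3, with the endpoint in Protocol 8.1.2.1, and with the SAP's own rows for SAEs, AESIs, withdrawals and deaths. Taken literally, it removes a defined class of AE eCRF records from the only tables that report SAEs and AEs leading to withdrawal. That is a contradiction to be resolved, not proof that events will be lost.

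The number affected cannot be derived and may be zero. Each subject matters little as a percentage, but SAE and related-SAE tables are read by count, and under the literal reading a single omitted event could separate none from one. The primary objectives and all hypothesis tests are untouched. The correction is cheap and belongs in the SAP before the tables are run.

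**What to change.** In SAP 13.3:

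- State that the SAE, related-SAE, AESI, AE-leading-to-withdrawal and death tables and overview rows include all AE eCRF records, solicited or unsolicited.
- Name the analysis set for them, for example the existing Overall Safety Set.
- Flag records that are on the AE eCRF only because of the Protocol 7.1.1 note, and leave them out of the general unsolicited-AE tables (any, related, by severity), since SAP 13.2 already counts them.
- Keep in those tables any reaction reclassified as unsolicited under the Day 14 rule, even if it was also serious or led to withdrawal. The protocol applies that rule after Day 14 and SAP 13.2 on Day 14; the flag needs one wording.
- Leave the 30-minute table unchanged. Its events precede eDiary recording, so SAP 13.2 does not capture them.

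Copying the protocol's scope sentence into the SAP would not be enough: it would bring these reactions into the general AE rows and still name no analysis set.

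The cost is a short paragraph in the SAP and one derived flag in the AE dataset. No new data are needed.

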13.4 Clinical Safety Laboratory Investigations

Not applicable

13.5 Concomitant Medication

Concomitant medications include all medications (including vaccines) taken by/administered to the subject at and after enrolment and must be documented on the Concomitant Medications eCRF (See protocol section 6.5 for definitions).

Medications (generic drug name) will be coded using the WHODRUG dictionary.

The frequencies and percentages of subjects reporting prior or concomitant medications will be tabulated by vaccine group and overall for All-Enrolled Set.

Summaries for concomitant medications will be presented by ATC level 2 code and preferred medication name, based on the All-Enrolled Set.

14. INTERIM ANALYSIS

There are no planned interim analyses for this study.

15. DATA MONITORING COMMITTEES

Not applicable

16. LIST OF FINAL REPORT TABLES, LISTINGS AND FIGURES

This list of tables, listings and figures are defined and combined with the table shells.

